- For analyses including double-blind treatment phase, the baseline for SBP, DBP, and pulse is defined as the last non-missing value before randomization. The rationale for using the last available value in the baseline period is to minimize the potential confound of discontinuing or dose stabilization of medications that modulate BP and pulse during the screening phase (which is early in the baseline period).
- Similarly, for other study phases, the baseline is defined as the last non-missing value before patients enter the study phases of interest. This baseline definition was chosen to be consistent with the analysis approach for double-blind treatment phase as described above.

This baseline definition for SBP, DBP, and pulse applies to all analyses (both continuous and categorical).

The baseline and postbaseline values for temperature and weight are defined below (Table CGAM.5.3):

- For continuous analyses of temperature and weight, last nonmissing baseline during the baseline period will be used as the baseline value.
- For the analyses of categorical changes of interest in temperature and weight,
 - the baseline is defined as the minimum value during baseline period when the direction is low
 - the baseline is defined as the maximum value during the baseline period when the direction is high

Table CGAM.5.6. Criteria for Treatment-Emergent, Potentially Clinical Significant and Categorical Changes and Sustained Elevation in Vital Signs and Weight

Parameter	Direction	Criteria	Patients Population defined by Baseline Categories
Systolic BP (mm Hg) (sitting)	Low	≤90 and decrease ≥20	>90; ≤90; All patients
	High	≥140 and increase ≥20	<140; ≥ 140; All patients
	PCS High	≥180 and increase ≥20	<180; ≥ 180; All patients
	Sustained Elevation	≥140 and increase ≥20 at 2 consecutive visits	<140; ≥ 140; All patients
Diastolic BP (mm Hg) (sitting)	Low	≤50 and decrease ≥10	>50; ≤50; All patients
	High	≥90 and increase ≥10	<90; ≥ 90; All patients
	PCS High	≥105 and increase ≥15	<105; ≥ 105; All patients
	Sustained Elevation	≥90 and increase ≥10 at 2 consecutive visits	<90; ≥ 90; All patients
Systolic BP or Diastolic BP (mm Hg) (sitting)	Sustained Elevation	Meeting criteria for systolic BP for 2 consecutive visits or meeting criteria for diastolic BP for 2 consecutive visits or both	All patients
Pulse (bpm) (sitting)	Low	<50 and decrease ≥15	≥50; <50; All patients
	High	>100 and increase ≥15	≤100; >100; All patients
	Sustained Elevation	>100 and increase ≥15 at 2 consecutive visits	≤100; >100; All patients
Weight (kg)	Low	(Loss) decrease ≥7%	All patients
	High	(Gain) increase ≥7%	All patients
Temperature (° F)	Low	<96° F and decrease ≥2° F	≥ 96° F
	High	≥101° F and increase ≥2° F	<101° F

Criteria for Treatment-Emergent, Potentially Clinical Significant and Categorical Changes and Sustained Elevation in Vital Signs and Weight (Abbreviations)

Abbreviations: BP = blood pressure; PCS = Potentially Clinically Significant; mm Hg = millimeters of mercury; bpm = beats per minute; kg = kilograms; °F = degrees Fahrenheit.

5.5.9.1.4. *Electrocardiogram Intervals and Heart Rate*

Analyses of QTc interval, Fridericia's corrected QT interval (QTcF) (msec), will be calculated with Fridericia's formula as $QT/RR^{1/2}$. For the QTc calculations, the unit for QT is milliseconds and the unit for RR is seconds. For patients with QRS ≥ 120 milliseconds at any time during the study, the QT and QTc interval will be excluded from the analyses. A listing of ECG data for patients with QRS ≥ 120 milliseconds at any time during the study will be provided.

The baseline for ECG is defined as the last non-missing baseline value during the baseline period. To be exact,

- For analyses including double-blind treatment phase, the baseline for ECG is defined as the last non-missing value before randomization. The rationale for using the last available value in the baseline period is to minimize the potential confound of discontinuing or dose stabilization of medications that modulate ECG during the screening phase (which is early in the baseline period).
- Similarly, for other study phases, the baseline is defined as the last non-missing value before patients enter the study phases of interest. This baseline definition was chosen to be consistent with the analysis approach for the double-blind treatment phase as described above.

This baseline definition for ECG applies to all analyses (both continuous and categorical, quantitative and qualitative).

The baseline and postbaseline values are summarized in [Table CGAM.5.3](#).

The number and percent of patients meeting criteria for treatment-emergent abnormalities in ECG intervals (PR, QRS, and QTcF) and heart rate at any time during study will be summarized. Treatment group comparisons will be performed using Fisher's exact test for SP III.

[Table CGAM.5.7](#) displays the criteria for treatment-emergent changes in ECG intervals and heart rate.

- For treatment-emergent low analyses: patients with normal or high values at baseline (no low values) will be included.
- For treatment-emergent high analyses: patients with normal or low values at baseline (no high values) will be included.
- For treatment-emergent increase analyses: patients with a baseline and at least one postbaseline result will be included.

Table CGAM.5.7. Criteria for Treatment-Emergent Changes in ECG Intervals and Heart Rate

Parameter	Direction	Criteria	
Heart Rate (bpm)	Low	<50 and decrease ≥ 15	
	High	>100 and increase ≥ 15	
PR Interval (msec)	Low	<120	
	High	≥ 220	
QRS Interval (msec)	Low	<60	
	High	≥ 120	
QTcF (msec)	Low	Males: <330	Females: <340
	High	Males: >450	Females: >470
	PCS High	>500msec	
	Increase	Increase >30 msec	
		Increase >60 msec	
		Increase >75 msec	

Abbreviations: bpm = beats per minute; ECG = electrocardiogram; PCS = Potentially Clinically Significant; QTcF = Fridericia's corrected QT interval.

In addition, qualitative ECG abnormalities will be evaluated which will include 11 ECG categories (axis, rhythm, conduction, ischemia, infarction, injury, morphology, U-waves, T-waves, ST Segment, and other abnormalities) of qualitative findings at any time postbaseline. A category is a collection of possible descriptions (findings) of one qualitative aspect of an ECG. A category name is the name of the qualitative aspect of the ECG (for example, rhythm, conduction, morphology, ischemia, and so forth). A finding is one of the possible specific descriptions (for example, sinus bradycardia, acute septal infarction) within a category.

A shift table summary of qualitative ECGs at any time will be produced, to assess shifts from baseline normal to postbaseline abnormal for the overall ECG and for each of the 11 finding categories mentioned above.

The summaries of the 11 ECG categories will exclude ECGs with any of the following: overall ECG could not be evaluated by the cardiologist, lead reversals or <9 leads, nonmatching demographic data, and those suggesting patient identification errors.

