5.5.1.6. Baseline and Postbaseline Definition

Table CGAM.5.3 describes the rules for determining the patient population and baseline and postbaseline observations for each study phase and type of analysis. When “last of Visit x-x” is used in the table, the last nonmissing observation obtained in the visit interval will be used.

Table CGAM.5.3. Patient Population with Baseline and Postbaseline Definitions by Study Phase and Type of Analysis

Study Phase / Analysis	Patient Population	Baseline Observation	Postbaseline Observation(s)
Study Phase III (Treatment Phase)			
Continuous secondary efficacy analyses (Repeated measures)	Patients in ITT population with a baseline and at least one postbaseline observation	Visit 3	All Visits 4–9
TEAEs	Safety population	All Visits 1–3 before dosing	Visit 3 after dosing – through Visit 9 before dosing if applicable
Serious Adverse Events, Discontinuations due to Adverse Events	Safety population	NA	Visit 3 after dosing – through Visit 9 before dosing if applicable
C-SSRS categorical analyses	Patients in safety population with a baseline and at least one postbaseline C-SSRS assessment	Recent History: All Visits 1–3 excluding lifetime ^a All Prior History: Visits 1–3 including lifetime ^a	All Visits 3.01–9
Treatment-emergent abnormal laboratory values	Patients in safety population with normal laboratory values at all nonmissing baseline visits (with respect to direction being analyzed) and who have at least one postbaseline observation	All Visits 1–3	All Visits 3.01–9
Treatment-emergent immunogenicity	Patients in safety population who are evaluable for TE ADA	Visit 3	All Visits 3.01–9
Treatment-emergent changes in vital signs and weight, ECG parameters	Patients in safety population with a baseline and at least one postbaseline observation	Last non-missing value from Visits 1–3 for BP, pulse and ECG All Visits 1–3 for weight and temperature	All Visits 3.01–9
Continuous safety analysis of vital signs, weight, laboratory and ECG parameters (box-whisker plot)	Safety population	Last non-missing value from Visits 1–3	Visits 4–9

Patient Population with Baseline and Postbaseline Definitions by Study Phase and Type of Analysis

Study Phase / Analysis	Patient Population	Baseline Observation	Postbaseline Observation(s)
Study Phase III and IV combined (Double-blinded and open-label extension phase combined)			

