Specifically, the following outcomes are C-SSRS categories and have binary responses (yes/no). The categories have been re-ordered from the actual scale to facilitate the definitions of the composite and comparative endpoints, and to enable clarity in the presentation of the results.

Category 1 – Wish to be Dead

Category 2 – Non-specific Active Suicidal Thoughts

Category 3 – Active Suicidal Ideation with Any Methods (Not Plan) without Intent to Act

Category 4 – Active Suicidal Ideation with Some Intent to Act, without Specific Plan

Category 5 – Active Suicidal Ideation with Specific Plan and Intent

Category 6 – Preparatory Acts or Behavior

Category 7 – Aborted Attempt

Category 8 – Interrupted Attempt

Category 9 – Actual Attempt (non-fatal)

Category 10 – Completed Suicide

Self-injurious behavior without suicidal intent is also a C-SSRS outcome (although not suicide-related) and has a binary response (yes/no).

Composite endpoints based on the above categories are defined below.

- Suicidal ideation: A “yes” answer at any time during treatment to any 1 of the 5 suicidal ideation questions (Categories 1-5) on the C-SSRS.
- Suicidal behavior: A “yes” answer at any time during treatment to any 1 of the 5 suicidal behavior questions (Categories 6-10) on the C-SSRS.
- Suicidal ideation or behavior: A “yes” answer at any time during treatment to any 1 of the 10 suicidal ideation and behavior questions (Categories 1-10) on the C-SSRS.

The following outcome is a numerical score derived from the C-SSRS categories. The score is created at each assessment for each patient and is used for determining treatment emergence.

- Suicidal Ideation Score: The maximum suicidal ideation category (1-5 on the C-SSRS) present at the assessment. Assign a score of 0 if no ideation is present.

For SP III, comparative endpoints of interest are defined below. “Treatment emergence” is used for outcomes that include events that first emerge or worsen. “Emergence” is used for outcomes that include events that first emerge.

- Treatment-emergent suicidal ideation compared to recent history:
An increase in the maximum suicidal ideation score during treatment (Visits 3.01 to 9 for SP III) from the maximum suicidal ideation category during the screening and lead-in periods (C-SSRS scales taken at Visits 1 to 3 excluding “lifetime” for SP III).
- Treatment-emergent suicidal ideation compared to all prior history:

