An increase in the maximum suicidal ideation score during treatment (Visits 3.01 to 9 for SP III) from the maximum suicidal ideation category prior to treatment (C-SSRS scales taken at Visits 1 to 3 including “lifetime” for SP III).
- Treatment-emergent serious suicidal ideation compared to recent history:
An increase in the maximum suicidal ideation score to 4 or 5 on the C-SSRS during treatment (Visits 3.01 to 9 for SP III) from not having serious suicidal ideation (scores of 0 to 3) during the screening and lead-in periods (C-SSRS scales taken at Visits 1-3 excluding “lifetime” for SP III).
- Treatment-emergent serious suicidal ideation compared to all prior history:
An increase in the maximum suicidal ideation score to 4 or 5 on the C-SSRS during treatment (Visits 3.01 to 9 for SP III) from not having serious suicidal ideation (scores of 0 to 3) prior to treatment (C-SSRS scales taken at Visits 1 to 3 including “lifetime” for SP III).

- Emergence of serious suicidal ideation compared to recent history:
An increase in the maximum suicidal ideation score to 4 or 5 on the C-SSRS during treatment (Visits 3.01 to 9 for SP III) from no suicidal ideation (scores of 0) during the screening and lead-in periods (C-SSRS scales taken at Visits 1 to 3 excluding “lifetime” for SP III). Recent history excludes “lifetime” scores from the baseline C-SSRS scale or Baseline/Screening C-SSRS scale.
- Emergence of serious suicidal ideation compared to all prior history:
An increase in the maximum suicidal ideation score to 4 or 5 on the C-SSRS during treatment (Visits 3.01 to 9 for SP III) from no suicidal ideation (scores of 0) prior to treatment (C-SSRS scales taken at Visits 1 to 3 including “lifetime” for SP III).
- Improvement in suicidal ideation at endpoint compared to baseline:
A decrease in suicidal ideation score at endpoint (the last measurement during treatment; Visits 3.01 to 9 for SP III) from the baseline measurement (the measurement taken just prior to treatment [last non-missing value taken at Visit 2 to Visit 3 for SP III]).
- Emergence of suicidal behavior compared to all prior history:
The occurrence of suicidal behavior (Categories 6 to 10) during treatment (Visits 3.01 to 9 for SP III) from not having suicidal behavior (Categories 6 to 10) prior to treatment (Visits 1 to 3 including “lifetime” for SP III).

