Above analyses was only described for SP III, for the analyses including SP IV and SP V, the baseline and postbaseline definition for each of the analyses above is summarized in [Table CGAM.5.5](#).

Table CGAM.5.5. Baseline and Post-Baseline Definition for Treatment-Emergent Suicidal Analyses for GMB-treated Population

Analyses	Study Phase	Baseline	Post-baseline

 Treatment-emergent suicidal ideation compared to recent history Treatment-emergent serious suicidal ideation compared to recent history Emergence of serious suicidal ideation compared to recent history 	III/IV	
Visit 1 to 3 excluding lifetime for GMB-treated patients in SP III;
 
Visit 1 to 9 excluding lifetime for placebo treated patients in SPIII.
	
Visits 3.01 to 22 for GMB-treated patients in SP III;
 
Visits 9.01 to 22 for placebo treated patients in SP III.

	III/IV/V	
Visit 1 to 3 excluding lifetime for GMB-treated patients in SP III;
 
Visit 1 to 9 excluding lifetime for placebo treated patients in SPIII.
	
Visits 3.01 to 24 for GMB-treated patients in SP III;
 
Visits 9.01 to 24 for placebo treated patients in SP III.

 Treatment-emergent suicidal ideation compared to all prior history Treatment-emergent serious suicidal ideation compared to all prior history Emergence of serious suicidal ideation compared to all prior history Emergence of suicidal behavior compared to all prior history 	III/IV	
Visit 1 to 3 including lifetime for GMB-treated patients in SP III;
 
Visit 1 to 9 including lifetime for placebo treated patients in SPIII.
	
Visits 3.01 to 22 for GMB-treated patients in SP III;
 
Visits 9.01 to 22 for placebo treated patients in SP III.

	III/IV/V	
Visit 1 to 3 including lifetime for GMB-treated patients in SP III;
 
Visit 1 to 9 including lifetime for placebo treated patients in SPIII.
	
Visits 3.01 to 24 for GMB-treated patients in SP III;
 
Visits 9.01 to 24 for placebo treated patients in SP III.

Improvement in suicidal ideation at endpoint compared to baseline	III/IV	
Last non-missing measure prior to or at visit 3 for GMB-treated patients in SP III;
 
Last non-missing measure prior to or at visit 9 for GMB-treated patients in SP III.
	
Last value during Visits 3.01 to 22 for GMB-treated patients in SP III;
 
Last value during Visits 9.01 to 22 for GMB-treated patients in SP III.

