Baseline and Post-Baseline Definition for Treatment Emergent Suicidal Analyses for GMB-treated Population

Analyses	Study Phase	Baseline	Post-baseline
	III/IV/V	Last non-missing measure prior to or at visit 3 for GMB-treated patients in SP III; Last non-missing measure prior to or at visit 9 for GMB-treated patients in SP III.	Last value during Visits 3.01 to 24 for GMB-treated patients in SP III; Last value during Visits 9.01 to 24 for GMB-treated patients in SP III.

Abbreviations: GMB = galcanezumab; SP = study phase.

Patients who discontinued from the study with no postbaseline C-SSRS value will be considered unevaluable for analyses of suicide-related events. Only evaluable patients will be considered in the analyses. Fisher's exact test will be used for treatment comparisons in SP III.

5.5.9.1.3. **Vital Signs and Weight**

Vital signs collected during the study include systolic and DBP, pulse, and temperature. Blood pressure and pulse measurements will be taken when the patient is in a sitting position. Three measurements of sitting BP and pulse will be collected at approximately 30 to 60 second intervals at every visit and the 3 sitting BP measurements and 3 pulse values will be averaged and used as the value for that visit.

Table CGAM.5.6 displays the criteria used to define treatment-emergent, potentially clinically significant changes and sustained elevation in vital signs and weight. The last column of the table displays the patient population for each analysis based on baseline categories. The number and percent of patients meeting these criteria will be summarized. Treatment group comparisons will be performed using Fisher's exact test for SP III.

The criteria to identify patients with treatment-emergent abnormal changes generally consist of 2 parts, an absolute threshold and a change from baseline amount.

- The absolute threshold in the criteria is based on 1) minimum postbaseline when the direction is low; 2) maximum postbaseline when the direction is high.
- The change from baseline amount in the criteria is 1) decrease from baseline (defined below and in Table CGAM.5.3) to minimum postbaseline when the direction is low; 2) increase from baseline (defined below and in Table CGAM.5.3) to maximum postbaseline when the direction is high.

The baseline for systolic blood pressure (SBP), DBP, and pulse is defined as the last non-missing baseline value during the baseline period (See Table CGAM.5.3). To be exact,

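### C-SSRS improvement in suicidal ideation: the denominator includes patients at score 0, who cannot improve, and this measure's row in Table CGAM.5.5 is mislabelled

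*SAP*

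**What the plan says.** **Numerator.** SAP Section 5.5.9.1.2 counts as improved any patient with "A decrease in suicidal ideation score at endpoint (the last measurement during treatment; Visits 3.01 to 9 for SP III) from the baseline measurement". For SP III the baseline is the "last non-missing value taken at Visit 2 to Visit 3 for SP III". The definition sets no condition on the baseline score. The score is the highest ideation category present, 1 to 5, with the rule "Assign a score of 0 if no ideation is present".

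**Denominator.** SAP Table CGAM.5.3 gives the SP III analysis set for C-SSRS categorical analyses as "Patients in safety population with a baseline and at least one postbaseline C-SSRS assessment". Section 5.5.9.1.2 adds: "Patients who discontinued from the study with no postbaseline C-SSRS value will be considered unevaluable for analyses of suicide-related events". It continues: "Only evaluable patients will be considered in the analyses". No narrower set is given for improvement.

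**Use.** Improvement is among the comparative measures that Section 5.5.9.1.2 presents and compares in SP III, by Fisher's exact test. It is also summarised for the galcanezumab-treated population over SP III/IV and SP III/IV/V. SAP Section 5.5.9.1 makes those latter summaries descriptive only.

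**Baselines for the combined phases.** In the improvement row of SAP Table CGAM.5.5, the second baseline line reads "Last non-missing measure prior to or at visit 9 for GMB-treated patients in SP III". The first baseline line (Visit 3) and both post-baseline lines carry the same patient label. This holds for III/IV and for III/IV/V.

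**The concern.** A patient who scores 0 before treatment cannot decrease. That patient is always in the denominator and never in the numerator. Protocol exclusion criterion 20 keeps out patients whom the investigator considers at significant risk for suicide, so baseline scores of 0 are probably common. That is an inference, since neither document gives a prevalence.

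A reader of the output will tend to take the percentage as the chance that a patient with ideation gets better. It is instead a product of two quantities, one of which (how many patients in the arm had ideation at baseline) has nothing to do with treatment. Section 5.5.9.1.2 sets no minimum event count for the Fisher test, so p-values may appear on very sparse tables.

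The SAP uses an at-risk set elsewhere. For ECG intervals it says: "For treatment-emergent low analyses: patients with normal or high values at baseline (no low values) will be included". Section 5.5.9.1.5 does the same for treatment-emergent laboratory values.

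In Table CGAM.5.5 the difficulty is one of programming. Followed to the letter, the row gives patients who started on galcanezumab two competing baselines, one of them after the whole double-blind phase on drug. It gives patients who switched from placebo no baseline.

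**Working it through.** The plan states no figure for this measure, so there is none to reproduce.

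**Inputs**
- N = 162 / 2 = 81 per arm (SAP Section 5.2: minimum of about 162, randomised 1:1). All are taken as evaluable.
- Score floor 0, and improvement is any decrease (Section 5.5.9.1.2).
- k, the number per arm with baseline score above 0: not in the documents. Assumed 2, 4, 8 or 16 of 81.
- r, the proportion of those k patients who improve: assumed.

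**Step 1: what the percentage is.** Reported % = 100 × (k / N) × r. Its ceiling, at r = 1, is 100 × k / N. Entries are expected values.

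| k of 81 | Ceiling | r = 75%, all evaluable | r = 75%, baseline > 0 |
|---|---|---|---|
| 2 | 2.5% | 1.9% | 75% |
| 4 | 4.9% | 3.7% | 75% |
| 8 | 9.9% | 7.4% | 75% |
| 16 | 19.8% | 14.8% | 75% |

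**Step 2: equal improvement, unequal baseline.** Take r = 75% in both arms.
- k = 8 v 4: 6/81 = 7.4% v 3/81 = 3.7%, two-sided Fisher p = 0.50.
- k = 12 v 4: 9/81 = 11.1% v 3/81 = 3.7%, p = 0.13.

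The reported percentages differ two- to three-fold although patients with ideation improve equally in both arms. Neither comparison is significant.

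**Step 3: dilution.** Take the most extreme contrast: k at risk per arm, all improving in one arm and none in the other.

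| k per arm | p, k/81 v 0/81 | p, k/k v 0/k |
|---|---|---|
| 3 | 0.25 | 0.10 |
| 4 | 0.12 | 0.029 |
| 5 | 0.059 | 0.008 |
| 6 | 0.028 | 0.002 |

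Even in this limiting case, among the k shown, the choice of denominator moves the result across 0.05 only at k = 4 or 5.

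**Step 4: Table CGAM.5.5 beside its parallels**

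| Place | Visit 3 line is for | Visit 9 line is for |
|---|---|---|
| Recent-history and all-prior-history rows | galcanezumab in SP III | placebo in SP III |
| Improvement row, III/IV and III/IV/V | galcanezumab in SP III | galcanezumab in SP III |

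Table CGAM.5.3 gives former placebo patients a C-SSRS baseline window of Visits 1 to 9 and post-baseline from Visit 9.01. Table CGAM.5.2 counts placebo patients who enter open label with at least one galcanezumab injection as part of the galcanezumab-treated population. The Visit 9 line was therefore evidently meant for placebo patients.

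Taken literally, the row would omit at most 81 of 162 patients (50%), if every placebo patient entered SP IV. If 70% entered (assumed), it would omit about 57 of 138 (41%).

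**Step 5: baseline window.** The SP III text takes the last value from Visit 2 to Visit 3. Table CGAM.5.5 takes the last value at or before Visit 3, which admits Visit 1. The two differ only for a patient with a Visit 1 score and none at Visits 2 and 3.

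**The case against.** The strongest reply is that the measure is correctly defined as it stands: the proportion of evaluable patients whose score fell. Patients at 0 are never counted as improved. Randomisation balances baseline ideation in expectation, and Fisher's test keeps its validity under no effect. All of this stands. A reader might infer that the percentages do not measure improvement at all. The documents do not support that: every patient in the numerator has a true decrease, and what is lost is interpretability and sensitivity.

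It can also be said that all-patient denominators are common in this SAP: weight change, QTcF increase, hepatic elevations and TEAEs. This stands only in part. Any patient can gain weight or lengthen QTcF, and the hepatic summaries are also split by baseline level. TEAEs are the nearer parallel, since an event already severe at baseline cannot worsen.

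A reader might extend the point to the emergence measures, which share the denominator. Their definitions already state the starting state. If most patients score 0, restricting them would barely change the denominators.

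A reader might also conclude that former placebo patients will be dropped, or that the SP III test is affected. Neither follows. The parallel rows make the intended label plain. Table CGAM.5.5 governs only the galcanezumab-treated summaries, while SP III has its own baseline in the text.

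Finally, improvement is not among the measures named in Protocol Section 12.2.10.3, and harm is covered by the category, composite and treatment-emergent measures. That is why the point is minor.

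**Conclusion.** The point holds as a minor one with two separate parts.

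First, the SP III improvement percentage and its Fisher test use all evaluable patients, including those who cannot decrease. The result equals baseline prevalence times the improvement rate, so differences are diluted and chance imbalance in baseline ideation enters the comparison. The size cannot be fixed from the documents. All k and r values above are assumptions, and 81 per arm assumes the minimum sample size with full evaluability. The illustrations show misleading percentages and lost sensitivity. They do not show a false positive, and with three or fewer patients at risk per arm neither denominator is informative.

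Second, the improvement row of Table CGAM.5.5 is mislabelled for III/IV and III/IV/V. The intended reading can be recovered, and only descriptive summaries are touched. The two baseline windows also differ.

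No primary or gated endpoint is affected.

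**What to change.** 1. In SAP Section 5.5.9.1.2, set the denominator for improvement to evaluable patients with baseline ideation score above 0. Optionally show n/N for all evaluable patients beside it. Baseline is measured before the first dose, so the SP III comparison remains between randomised groups.
2. In the improvement row of Table CGAM.5.5, for III/IV and III/IV/V, relabel the Visit 9 baseline line and the Visits 9.01 to 22 and 9.01 to 24 post-baseline lines as applying to patients treated with placebo in SP III.
3. State one baseline window for improvement, so that the SP III text and Table CGAM.5.5 agree on whether a Visit 1 score may serve.

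No added restriction on the emergence measures is needed. The cost is a few lines of SAP text and one filter in the C-SSRS program. The drawback is a small denominator, possibly only a few patients per arm, so counts should be read alongside any p-value.
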